## **7. DATA CONVENTION**

### **7.1 Data Handling Convention for Dropouts or Missing Data**

For each summaries, only observed data will be used. Unless otherwise specified missing data will not be imputed. Unless otherwise specified, summary statistics will be calculated as long as one non-missing value exists.

For AE start and/or end date missing or partial missing, the AE will be treated as TEAE if it cannot be determined a non-TEAE. If severity or relationship is found to be missing the most severe occurrence will be imputed for the particular summary.

## 7.2 Analysis Visit Window

The derived analysis visit windows are outlined in Table below.

**Table 3 Derived Analysis Visit Windows**

Visit		Nominal day	Window
1	Week 12 (Baseline)	NA	NA
2	Week 20	Day 141	Day 113 to 169
3	Week 28	Day 197	Day 170 to 239
4	Week 40	Day 281	Day 240 to 323
5	Week 52	Day 365	Day 324 to 407
6	Week 64	Day 448	Day 408 to 462
7	Week 68 (FU)	Day 476	NA

The analysis visits are derived according to the following criteria:

- The unscheduled visits are not used for the deriving.
- If a study visit is the only one in an analysis window, this study visit becomes the derived analysis visit.
- If there are multiple visits in a visit window, the closest visit to the nominal day becomes the analysis visit. In the event that two visits are the closest visits to the nominal day and equally distanced to the nominal day, the visit after the nominal day becomes the derived visit.
- Unless otherwise specified, the baseline values are the last available assessment before the first dose of study A02.
- The follow-up visit will not be derived. The study visit will be used.
- Unscheduled visits and retests (same visit number assigned), will not be displayed in by-visit summary tables, but will be included in the data listings. All data will be listed. Listings will include treatment, scheduled, unscheduled, retest and early discontinuation data.
- The efficacy endpoints based on diary data use different windows. See Section 7.3.3.1.

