4.5.2 Discontinuation from study

Subjects may withdraw from the study for any reason. The Investigator will discontinue a subject from the study if ANY of the following criteria are met:

- The subject wishes to voluntarily withdraw from the study
- The subject is lost to follow-up
- The subject is diagnosed with breast cancer
- The subject experiences elevated ALT or AST $>3 \times$ ULN and a total bilirubin $>2 \times$ ULN (such subjects should be treated per standard of care and followed till resolution.)
- The subject has endometrial thickness of ≥ 5 mm as measured by transvaginal ultrasound at Week 12, assessed centrally (subject with insufficient imaging data will have repeat transvaginal ultrasound)
- The subject has an abnormal endometrial biopsy result at Week 12, as assessed by the endometrial biopsy adjudication committee.
- The subject has endometrial thickness of ≥ 5 mm as measured by transvaginal ultrasound conducted at any time during the study based on investigator's judgement. (The images may be requested for central assessment.)
- The subject has an abnormal result from an endometrial biopsy conducted at any time during the study based on Investigator's judgement. (The biopsy report or slides may be requested for central assessment)
- Continuing the subject in the study off treatment would be detrimental to the subject's safety in the opinion of the Investigator

If a subject is discontinued prematurely from the study, the date the subject is withdrawn from the study and the reason for withdrawal will be recorded on the eCRF.

In case of discontinuation from study, the end of treatment (EOT) visit assessments should be performed, as far as possible (Sections 5.2.1.3 and 5.2.2) and any unresolved AEs or SAEs will be followed up according to Section 8.10.

The Investigator must make every effort to contact the subject to review all AEs. In the event that a subject discontinues from the study at any given time, the reason for discontinuation must be fully documented in the source documents and the eCRF. The Investigator and or site personnel will document the AEs and any other assessments in

the source documents and will make every effort to complete all required EOS assessments.

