5.2.5 Unscheduled visits

An unscheduled visit is defined as any visit to the Investigator site outside of the protocol specified study site visits due to safety reasons or when a repeat test and/or measurement is required (e.g., obvious measurement errors, measuring device failure, confirmation of out-of-range results), where the subject is seen by study personnel.

Additional unscheduled samples for safety assessments may be performed at the discretion of the Investigator, if deemed necessary. All unscheduled visits and assessments performed during the visits will be recorded in the eCRF.

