10 STATISTICAL METHODS AND PLANNED ANALYSES

10.1 Determination of sample size and randomization

There is no formal estimation of sample size for inclusion of subjects in Study MT-8554-A02. It is planned to enroll up to 364 subjects who have completed Study MT-8554-A01 and who comply with all eligibility criteria for Study MT-8554-A02.

Study MT-8554-A02 is an open-label extension study of Study MT-8554-A01. All subjects will receive MT-8554 (was 10 mg initially, switched to 5 mg) for 52 weeks. Subjects will not be randomized.

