#### **8.2.7.1 Endometrial Thickness Measured by Transvaginal Ultrasound (TVU)**

The endometrial thickness as measured by TVU will be summarized in the tables by treatment group of A01 and overall and visit as below. (Table 14.3.6.1, Table 14.3.6.2)

1. Summary table presenting mean and SD for baseline, post baseline visits and change from baseline
2. Summary table of endometrial thickness by category (<5 mm, 5 to 8 mm, >8 mm)
3. Summary table for category of change from baseline (>3 mm, >5 mm)

The central reading data will be used for the analysis.

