### 8.2.7.2 Endometrial Histology (Endometrial Biopsy)

The Endometrial biopsy data will be summarized in the tables by treatment group of A01 and overall and visit as below.

1. Summary tables of proportion of subjects in abnormal\* category (Table 14.3.7.1)
2. Shift table for change in abnormal category from baseline to week 64 or EOT(Table 14.3.7.2)

\*Note: The histological categories are based on 2003 draft FDA guidance. [REDACTED]

[REDACTED]

[REDACTED]

[REDACTED]

The data from adjudication committee will be used for the analysis.

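### Hyperplasia found only on a for-cause biopsy between Week 12 and end of treatment can be missing from the tabulated incidence endpoint

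*SAP*

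**What the plan says.** Protocol 2.2.1 and SAP 2.2.1 list hyperplasia incidence, measured by biopsy, among the primary safety endpoints, without tying it to a visit. Protocol 6.5.5 and 6.5.6 schedule scans and biopsies at Week 12 and at Week 64 or early termination, for women with a uterus.

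The protocol foresees other procedures. Section 4.5.1 sends women with unexplained uterine bleeding for specialist investigation. One discontinuation criterion in 4.5.2 reads "The subject has an abnormal result from an endometrial biopsy conducted at any time during the study based on Investigator's judgement", followed by "The biopsy report or slides may be requested for central assessment". A parallel criterion covers scans, with the same optional wording for images. Section 5.2.5 classes as unscheduled any off-schedule site visit made for safety reasons or "when a repeat test and/or measurement is required (e.g., obvious measurement errors, measuring device failure, confirmation of out-of-range results".

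SAP 7.2 does not use unscheduled visits to derive analysis visits, and adds: "Unscheduled visits and retests (same visit number assigned), will not be displayed in by-visit summary tables, but will be included in the data listings". SAP 8.2.7.1 and 8.2.7.2 define the endometrial tables by visit. For biopsies, "The data from adjudication committee will be used for the analysis"; for scans, "The central reading data will be used for the analysis". SAP 8.2.7 makes no exception for unscheduled endometrial data and says only that all of it will be listed.

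**The concern.** The endpoint is an incidence over the extension, but the tables show what was found at two scheduled points. Two separate filters stand between a for-cause biopsy and those tables: the visit rule in SAP 7.2, and the restriction to adjudicated data when adjudication of that biopsy is optional. Removing one filter leaves the other.

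The records affected are not a random subset. For-cause procedures are done because something prompted them, such as bleeding, so leaving them out pushes the tabulated incidence down. Few cases would be expected in a table of this kind, so a single omission can decide whether the report shows none or some.

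**Working it through.** **The plan's own figure.** There is none to reproduce. Protocol 10.1 says: "There is no formal estimation of sample size for inclusion of subjects in Study MT-8554-A02". No expected hyperplasia rate, precision target or number of women with a uterus is given. The documents give only enrolment of up to 364 and about 100 completers.

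**Tracing one case.** Take a woman whose hyperplasia is found on a biopsy for bleeding at about Week 34.

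1. Week 34 is not a scheduled biopsy visit (Protocol 6.5.6). If she is seen at the site, the visit is unscheduled under 5.2.5. If the biopsy is done by the specialist, it is not a scheduled study visit either.
2. SAP 7.2 does not let an unscheduled visit become an analysis visit and keeps it out of by-visit tables.
3. Table 14.3.7.1 (proportion abnormal) is by visit. Table 14.3.7.2 (shift) runs from baseline to Week 64 or EOT. The Week 34 result enters neither.
4. If the visit rule were lifted, only adjudicated data would be analysed (SAP 8.2.7.2), and Protocol 4.5.2 does not require her slides to be sent.
5. An abnormal any-time biopsy is a discontinuation criterion, and discontinuation calls for EOT assessments, which include a biopsy (Protocol 4.5.2, 5.2.1.3). These are to be done only so far as possible. If the EOT biopsy is done and shows hyperplasia, she is tabulated; if not, she contributes no case.

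Early EOT biopsies meet a further gap. The post-baseline windows in SAP Table 3 start at Day 113 and end at Day 462. Days 86 to 112 (112 − 86 + 1 = 27 days) and days after 462 have no window. An early-termination biopsy on those days has no derived visit, unless it enters through the EOT column of the shift table.

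**Central reading.** Protocol 6.5.6, 8.8 and 11.4 describe central processing and adjudication by three pathologists, with no carve-out for off-schedule samples. Section 4.5.2 makes it optional for any-time procedures. The status of for-cause slides is therefore not consistent.

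**Size, as an illustration.** The denominator n (women with a uterus and a post-baseline biopsy) is assumed, with a range of 50 to 200. Exact (Clopper-Pearson) two-sided 95% limits:

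- 0 of n: upper limit = 1 − 0.025^(1/n). For n = 70, 1 − 0.025^(1/70) = 5.13%.
- 1 of n: lower limit = 1 − 0.975^(1/n). For n = 70, 0.04%.
- 1 of n: upper limit solves (1 − p)^n + n·p·(1 − p)^(n−1) = 0.025. For n = 70, 7.70%.

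| Assumed n | One case counted (95% CI) | Case omitted (95% CI) |
|---|---|---|
| 50 | 2.0% (0.05% to 10.65%) | 0% (0 to 7.11%) |
| 70 | 1.4% (0.04% to 7.70%) | 0% (0 to 5.13%) |
| 100 | 1.0% (0.03% to 5.45%) | 0% (0 to 3.62%) |
| 200 | 0.5% (0.01% to 2.75%) | 0% (0 to 1.83%) |

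This shows the effect of one omission. It does not estimate how likely one is.

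**The case against.** Keeping unscheduled records out of by-visit tables, with full listings, is a common display convention, and this is a single-arm descriptive study. The case would not vanish. It is listed; a finding judged clinically significant is an adverse event (Protocol 8.8) and enters the TEAE tables (SAP 8.2.1); discontinuation reasons are tabulated (SAP 8.1.1); and discontinuation calls for an EOT biopsy. All of that stands. But none of these outputs is the adjudicated incidence with a denominator, and each depends on a judgement or on a second biopsy being done and still positive.

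Parts of the SAP's adverse event list (8.2.1) and of the biopsy section (8.2.7.2) are redacted, and the adjudication charter is not available. An any-time summary, or a rule on for-cause slides, could be there. This limits certainty.

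A reader might go further in three ways that the documents do not support.

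- *Repeats are not read centrally, and an invalid result stays as baseline.* The repeat the protocol orders ("subject with insufficient imaging data will have repeat transvaginal ultrasound") belongs to the Week 12 criterion, which is assessed centrally. Protocol 10.3.1 takes baseline as the last valid value before the first A02 dose, and SAP 7.2 as the last available one, so a repeat done before dosing can be baseline. Only a repeat after dosing is shut out of that role. The retest rule does still apply at post-baseline visits.
- *The women at highest risk are removed from the analysis.* The rule omits records, not women.
- *The EOT biopsy will be normal because the lesion has been treated.* Nothing in the documents places treatment before that biopsy.

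**Conclusion.** The point holds for for-cause procedures. On the unredacted text, hyperplasia seen only on a for-cause biopsy between Week 12 and EOT adds nothing to Table 14.3.7.1 or 14.3.7.2, so a primary safety endpoint can be understated in the reassuring direction. Excluded scans affect the thickness tables, not hyperplasia.

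The size rests on two assumptions that the documents cannot confirm: the denominator, and that a case is missed at all. One omission moves the point estimate by 0.5 to 2.0 percentage points over 50 to 200 women, always to zero. With 70 women the upper limit falls from 7.7% to 5.1%. The conclusion also assumes that no redacted text supplies the missing summary.

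**What to change.** 1. **SAP 8.2.7.2.** Add a subject-level row to Table 14.3.7.1 for hyperplasia or worse on any biopsy after the first A02 dose, counting scheduled, early-termination and unscheduled biopsies. The denominator is women with a uterus and at least one post-baseline biopsy; give an exact 95% CI. Add a worst post-baseline row to Table 14.3.6.2 for thickness.
2. **Protocol 4.5.2 against 6.5.6, 8.8 and 11.4.** Reconcile these so that for-cause slides and images, where obtainable, go to the existing committee and central reader. Where they cannot be obtained, report locally read cases separately.
3. **SAP 7.2.** At post-baseline visits, let a valid repeat replace an insufficient or erroneous result. Keep baseline as the last valid value before the first A02 dose; a post-dose scan should not serve as baseline.

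The cost is a few sentences in the SAP, a protocol clarification and some extra central reads. Their number is unknown, and slides held by outside specialists may take effort to retrieve. For-cause sampling is not uniform across women, so the any-time row should stand beside the scheduled-visit result and not replace it. SAP section 4 has the plan finalised before database lock, so the SAP changes belong before that point.

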## 7.3 Definition of Analysis Variables

### 7.3.1 Study Subjects

#### 7.3.1.1 BMI

$$\text{BMI (kg/m}^2\text{)} = \text{Body weight (kg)}/\{\text{Body height (m)}\}^2$$

It will be rounded off the second decimal place and reported the value to the first decimal place.

#### 7.3.1.2 Medical history

All medical and surgical history will be coded from the actual term using the MedDRA version 20.1.

Medical and surgical history data collected in study A01 will be used.

### **7.3.1.3 Concomitant medications**

Concomitant medication is defined as any medication, other than study medication, which is taken on or after the start day of study A02 treatment.

All concomitant medications will be coded using the WHO drug dictionary (WHO Herbal Dictionary) (Version SEP 2017).

### **7.3.1.4 Duration of exposure and Cumulative Dosing Count**

The duration of exposure is calculated as the total number of days that the subject has been treated with study A02 medication—that is, from the study A02 treatment start date to the date of their EOT/withdrawal visit. For subjects lost to follow up, the treatment end date is taken to be the date of their last visit. Interruptions, compliance, and dose changes are not taken into account for duration of exposure.

Duration of exposure (days) = date of end of treatment visit – date of first dose of study A02 medication; Cumulative Dosing days= Duration of exposure – number of days subject miss the medication.

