4.5 Withdrawal of individual subjects

4.5.1 Discontinuation from treatment

Investigators may choose to temporarily or permanently discontinue study treatment for any reason, including AEs or tolerability.

If any clinically significant abnormality is detected on the clinical breast exam (see Section 6.5.2) at baseline or anytime during the study or there is any occurrence of unexplained uterine bleeding, study medication should be discontinued and subject should be referred to the specialists for further investigations per current standards. If all the required investigations such as physical examination of the breast, imaging and pathology are negative and available within 6 weeks, subject can resume study medication.

An unscheduled study visit can be used to reassess subject's symptoms and willingness to resume study drug.

If treatment is discontinued and the subject is not willing to resume study medication, every effort should be made to continue the subject on study, e.g., attending study visits and carrying out study procedures through to the final visit. For subjects declining to continue on the study, see Section 4.5.2.

The Suspension interval (start and end dates of suspension) and reason for suspending treatment must be recorded in source documents and the electronic Data Collection Form (eCRF).

Subjects who become pregnant during the study should be withdrawn from study treatment. Also see Section 8.8 for necessary documentation and procedures for following up with the subject.

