5 STUDY PLAN

Study assessments are summarised in the Time and events schedule (Table 1).

Table 1 Schedule of Assessments

Study Period	Open-label extension						Follow-up
Visit Number	Visit 1 ¹	Visit 2	Visit 3	Visit 4	Visit 5	Visit 6 (EOT)	Visit 7 (EOS)
Study Week ²	Week 12 ³	Week 20	Week 28	Week 40	Week 52	Week 64 ⁴	Week 68 ⁵
Study Day ±Window ²	Day 85 ±3	Day 141 ±7	Day 197 ±7	Day 281 ±7	Day 365 ±7	Day 448 ±7	Day 476 ±7
Informed consent	X						
Inclusion/exclusion criteria	X						
Physical examination ⁶	X	X	X	X	X	X	
Breast examination	X						X
Body weight	X			X			X
Vital signs ⁷	X	X	X	X	X	X	
12-lead ECG	X			X			X
Routine lab tests	X	X	X	X	X	X	
Transvaginal ultrasound ⁸	X						X
Endometrial biopsy ⁸	X						X
Reproductive hormones ⁹	X						X
PHQ-8 and GAD7	X		X				X
VMS diary	↔						
MENQOL	X		X			X	
Dispensing MT-8554 ¹⁰	X	X	X	X	X		
Drug accountability	X	X	X	X	X	X	
Adverse events	↔						
Concomitant medication	↔						
Compliance █ Calls to Subjects ¹¹	↔						

Abbreviations: ECG=Electrocardiogram; EOS=End of Study; EOT=End of Treatment Visit; GAD7=Generalized Anxiety Disorder-7 Questionnaire; MENQOL=Menopause Specific Quality of Life; PHQ-8=Eight-Item Patient Health Questionnaire; VMS=vasomotor symptoms.

1. Visit 7 (Week 12) of Study MT-8554-A01 will be considered Visit 1 of Study MT-8554-A02.
2. Study weeks and study days are in reference to the randomization performed on Day 1 in Study MT-8554-A01.
3. Assessments already carried out at Week 12 of Study MT-8554-A01 will not be repeated.
4. The EOT should be performed for subjects who complete treatment as well as those who withdraw from the study early.
5. The Follow-up visit, EOS, will be conducted by phone 30 days after the EOT visit for subjects who complete as well as those who withdraw early from the study.
6. Physical examination (abdominal, cardiovascular, general appearance, respiratory, and other) will be performed.
7. Vital signs (including sitting blood pressure, pulse rate, and tympanic body temperature) will be measured at all visits.

8. Transvaginal ultrasound and endometrial biopsy to be performed only on subjects who have a uterus. Pelvic examination will be performed only with endometrial biopsy.
9. Luteinizing hormone (LH), follicle stimulating hormone (FSH) and estradiol (E2) will be measured.

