5.2.2 Follow-up

5.2.2.1 Visit 7: Follow-up Visit (FU, Week 68 or 4 weeks after early termination)

Subjects who complete the study (or subjects who withdraw from treatment early) will be telephoned by the Investigator (or designee) 30 days after EOT, for a Follow-up visit. Information on any new AEs, follow-up on existing AEs, and prior/concomitant medication will be recorded.

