#### **8.1.5 Study Medication Exposure**

Duration of exposure to study medication in days will be summarized in table and presented in data listing for the SAF population. (Table 14.1.5)

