#### **8.1.6 Treatment Compliance**

Compliance to study medication will be presented for the ITT population in table. (Table 14.1.6)

All study medication administration and accountability data will be listed by subject.

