### 8.4 Dose Change

All subjects were treated with MT-8554 10 mg initially. Then from protocol amendment 4, all subjects remaining in study changed to MT-8554 5 mg. Some subjects already completed or discontinued the study. To compare the data before and after the dose change, the following analyses will be conducted.

No.	Title of Table	Analysis Population
14.1.5	Summary of Exposure to Study Medication: Duration of exposure the dose change	SAF
14.3.1.1	Summary of Treatment Emergent Adverse Events (TEAE)	SAF
14.3.1.1.Ex4Site	Summary of Treatment Emergent Adverse Events (TEAE -Exclude 4 Florida site-	SAF

No.	Title of Table	Analysis Population
14.3.1.2	Incidence of Treatment Emergent Adverse Events by System Organ Class, Preferred Term	SAF
14.3.1.2.Ex4Site	Incidence of Treatment Emergent Adverse Events by System Organ Class, Preferred Term -Exclude 4 Florida site-	SAF
14.3.1.4	Incidence of Treatment Emergent Adverse Events by System Organ Class, Preferred Term and Severity for before the dose change	SAF
14.3.6.1	Transvaginal Ultrasound (TVU)	SAF
14.3.6.1. Ex4Site	Transvaginal Ultrasound (TVU) -Exclude 4 Florida site-	SAF
14.3.6.2	Transvaginal Ultrasound (TVU) - Endometrial Thickness	SAF
14.3.6.2. Ex4Site	Transvaginal Ultrasound (TVU) - Endometrial Thickness -Exclude 4 Florida site-	SAF

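### Duration of exposure runs to the EOT or withdrawal visit and ignores interruptions, so time off drug can be reported as exposure, and dosing days are not planned for the exposure table

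*SAP*

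**What the plan says.** SAP 7.3.1.4 introduces duration of exposure as the number of days a woman has been treated with A02 medication. The operational rule is different. Time is counted "from the study A02 treatment start date to the date of their EOT/withdrawal visit", as EOT visit date minus first A02 dose date, or to the last visit for women lost to follow-up. The section adds: "Interruptions, compliance, and dose changes are not taken into account for duration of exposure". It also defines Cumulative Dosing days, which is duration minus missed days. SAP 7.3.1.5 uses that quantity as the numerator of the compliance percentage.

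For the tables, SAP 8.1.5 says "Duration of exposure to study medication in days will be summarized in table" (Table 14.1.5, Safety population) and mentions no dosing days. SAP 8.1.6 says "Compliance to study medication will be presented for the ITT population in table" (Table 14.1.6). The version excluding the four Florida sites, in SAP 8.5, uses the Safety population. SAP 8.4 lists a dose-change table titled "Summary of Exposure to Study Medication: Duration of exposure the dose change".

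Protocol 4.5.1 permits temporary or permanent stopping of treatment. For women who will not resume, it asks that every effort be made to keep them on study, "attending study visits and carrying out study procedures through to the final visit". Footnote 4 of protocol Table 1 says of the EOT visit: "The EOT should be performed for subjects who complete treatment as well as those who withdraw from the study early". Protocol 5.2.2.1 speaks of "subjects who withdraw from treatment early) will be telephoned by the Investigator (or designee) 30 days after EOT".

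**The concern.** The label and the formula measure different things. A visit date is not a dosing date, and this protocol deliberately creates time on study without drug, through interruptions and through follow-up after a permanent stop. The formula credits that time as exposure.

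The primary objective is long-term safety and tolerability, and Table 14.1.5 is where a reader will look for how long women took the drug. If it shows time on study, the safety results appear to rest on more drug exposure than was given. The planned tables do not let the reader correct this. The main compliance table covers a different population, since ITT requires a post-baseline exploratory assessment (SAP Table 2). The by-subject listings are not a summary. The SAP also does not say whether days after a permanent stop count as missed days.

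The dose-change version has a further gap. SAP 8.4 sets out to compare data before and after the switch from 10 mg to 5 mg. The exposure definition disregards dose changes, and no date is given for dividing the two periods.

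**Working it through.** The plan states no exposure figure to reproduce, so its formula is applied to its own schedule.

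**Inputs.** First A02 dose on Day 85 and EOT on Day 448 (nominal days, Table 1 of both documents). Planned treatment is 52 weeks, or 364 days (protocol synopsis). Dosing is once daily at bedtime (protocol 7.2). Six weeks, or 42 days, is the time within which drug may be resumed after a breast or bleeding work-up (protocol 4.5.1).

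**SAP formula.** 448 − 85 = 363 days for any woman whose EOT visit is on Day 448, whatever her dosing. This is one day short of 364.

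**Compliant completer.** First dose on the evening of Day 85, last on the evening of Day 447: 447 − 85 + 1 = 363. The formula gives the right answer for her.

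**One 6-week interruption.** 363 − 42 = 321 days dosed. 42/321 = 13.1% overstatement for that woman.

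**Permanent stop, EOT held on Day 448.** The last dose is taken on the evening before the visit shown. Days on drug = last dose day − 85 + 1.

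| Stop before | Last dose | Days on drug | Recorded | Recorded/on drug |
|---|---|---|---|---|
| Week 20 | Day 140 | 56 | 363 | 6.5 |
| Week 28 | Day 196 | 112 | 363 | 3.2 |
| Week 40 | Day 280 | 196 | 363 | 1.9 |
| Week 52 | Day 364 | 280 | 363 | 1.3 |

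**Group mean.** The documents give no rates, so the share *p* of women affected is assumed to be 5% to 20%, with all women reaching Week 64.

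*Assumption A: women who stop drug but stay on study have EOT at Week 64.* Each stops after 182 days (26 weeks, also assumed). True mean = 363 − *p* × (363 − 182).
- *p* = 0.05: 363 − 9.05 = 353.95; 363/353.95 − 1 = 2.6%.
- *p* = 0.20: 363 − 36.2 = 326.8; 363/326.8 − 1 = 11.1%.

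*Assumption B: EOT is held when treatment stops, so only interruptions are miscounted.* Each affected woman has one interruption of 42 days. True mean = 363 − *p* × 42.
- *p* = 0.05: 363 − 2.1 = 360.9; 363/360.9 − 1 = 0.6%.
- *p* = 0.20: 363 − 8.4 = 354.6; 363/354.6 − 1 = 2.4%.

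**Which reading of EOT applies.** Footnote 4 ties EOT to completing treatment or leaving the study. With protocol 4.5.1, that puts EOT at Week 64 for a woman who stops drug and stays. Protocol 5.2.2.1 counts 30 days from EOT for women who leave treatment early, which can place EOT at the stop of treatment. The SAP does not choose between them.

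**The case against.** The strongest reply is that nothing is hidden and the effect is modest. The SAP states its interruption rule openly and defines the net measure in the same section. A duration that ignores interruptions can stand as a descriptive measure, and it is exact for compliant completers. The large single-woman figures depend on one reading of EOT. Besides protocol 5.2.2.1, protocol section 8 counts follow-up from the last treatment visit, and SAP 7.3.1.4 itself speaks of a treatment end date. The 5% to 20% shares, the 182-day stop and universal follow-up to Week 64 are assumptions. The study is to finish at about 100 completers from up to 364 women, so follow-up will often be shorter. No exposure-adjusted event rate is visible in the SAP, compliance is tabulated, administration data are listed, and table shells that might show dosing days are not available to check.

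Much of this stands as a limit on size. The EOT question is a protocol ambiguity, and the group figures are illustrations. The 42 days is the limit for one trigger only; other interruptions have no stated limit and may be shorter or longer.

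It does not remove the fault. The mismatch between label and formula remains. Interruptions are credited under either reading, and the text and table titles point to duration alone. Compliance in ITT cannot be paired directly with exposure in the Safety population. The protocol's use of an unscheduled visit for the dose switch (7.4) makes a split date for each woman identifiable, but the SAP does not adopt it.

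**Conclusion.** The concern holds. As written, SAP 7.3.1.4 can report time on study as time on drug, and the planned exposure table offers no correction. For one woman the error ranges from 42 days (a 6-week interruption) to 307 days (363 − 56, last dose on Day 140 with EOT on Day 448). For the group mean it is 9 to 36 days under Assumption A and 2 to 8 days under Assumption B, conditional on the assumed rates. The true number of women affected is not in the documents. The size therefore depends mainly on how EOT is timed for women who stop drug but stay, and the protocol passages on that must be reconciled. This does not invalidate the study, but it should be corrected before database lock because the table supports the primary objective.

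**What to change.** 1. In SAP 7.3.1.4, define duration of exposure as last A02 dose date − first A02 dose date + 1. This works under either reading of EOT and leaves compliant completers at 363 days.
2. Define Cumulative Dosing days as that duration less recorded suspension intervals and other missed days, without double counting.
3. Report both rows in Table 14.1.5 for the Safety population, overall and before and after the dose change. Duration ignoring interruptions can stay as the first row, because the second shows the difference.
4. State the split date for SAP 8.4. Each woman's own switch to 5 mg, which protocol 7.4 places at an unscheduled visit, is the natural choice.
5. Say which denominator SAP 7.3.1.5 keeps for compliance. Its formula names the EOT visit date separately, so changing 7.3.1.4 alone would leave the two sections inconsistent.

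The cost is minor SAP wording and programming. Protocol 4.5.1 and 7.2.1 already require suspension dates and departures from the dose regimen in the eCRF, and SAP 8.1.6 already lists administration data by subject. Reported exposure will look slightly less favourable.
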